# 7 STUDY DESIGN

DEPICT is a multi-disciplinary mixed-methods study comprising four linked work streams culminating in a series of workshops (See Appendix A for Study Flow Diagram):

A. Quantitative analysis of national paediatric intensive care audit data (PICANet) linked to routine administrative data (Hospital Episode Statistics in England and Patient Episode Database for Wales), death registrations (Office of National Statistics) and adult critical care data (Case Mix Programme).

[This analysis will be conducted retrospectively using data collected as part of national audit during a 3-year period between 2014 and 2016].

- B. Qualitative and questionnaire study involving interviews of parents of critically ill children transported to PICU (and children themselves, where feasible); interviews with clinicians working in PICUs, PICRTs and acute general hospitals and service managers/commissioners; and questionnaires to collect feedback from parents of transported children.
   [This workstream will involve prospective recruitment of patients over a 12-month period in 2017-18].
- C. Health economic evaluation of the costs and value for money of different models of PICRTs to identify cost-effective models of service delivery.
   [This workstream will involve analysis of costs and children's outcomes collected as part of the previous workstreams].
- D. **Mathematical modelling**, including the use of location-allocation optimisation, to explore the potential clinical and cost impact of alternative models of service and geographical locations where PICRTs could be based.

[This workstream will involve modelling using the findings of the previous workstreams].

E. **Workshops** involving key stakeholders: children and young people, parents, clinicians, and service managers/commissioners.

The study will involve the participation of all 10 PICRTs and 24 PICUs in England and Wales (representing 21 individual NHS Trusts).

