#### 8.1.3.1 Clinical outcomes

Primary outcome: Mortality within 30 days following PICU admission (the first admission in case of multiple PICU admissions), established by data linkage with death registrations.

Secondary outcomes to include:

- a) Mortality at fixed time-points (PICU discharge, 90 days and 1 year following [first] PICU admission)
- b) Number of PICU admissions during study period and time to readmission (if applicable)
- c) Length of stay in PICU (number of days from PICU admission to discharge, for each PICU admission)
- d) Resource use in PICU (number of days of invasive ventilation, vasoactive agent therapy, renal replacement therapy and extra-corporeal life support during PICU stay, for each PICU admission)
- e) Length of hospital stay linked to the first PICU admission (number of days from hospital admission to hospital discharge)
- f) Number of A&E attendances in the 12 months following discharge from the first PICU admission
- g) Hospital resource use (total number of days admitted to hospital) in the 12 months following discharge from the first PICU admission.

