## 2) Draw inferences regarding the effect of key factors on patient outcome

Before any modelling work is undertaken, we will do a thorough descriptive analysis of the datasets and look for potential issues that would need to be addressed at an early stage, such as a large proportion of missing data for key confounders or an unusual distribution of age/weight/diagnosis or other risk factors. Prior to multivariate modelling, we will explore univariate associations between key explanatory variables (timeliness, care delivered) and potential confounders with our stated primary and secondary outcomes. All explanatory variables and confounders with significant univariate association with outcome will be considered in the regression modelling for Models 1 and 2. We will develop statistical models to study the association between timeliness of access to intensive care and clinical outcomes, and the association between care delivered by PIC retrieval teams and clinical outcomes. Since we recognise that the data could potentially be clustered by PICRT, we will develop multilevel models as appropriate (to include the random effects of PICU/PICRT/general hospital) depending on the outcome:

- Mortality at fixed time-points: logistic regression
- Length of stay (PICU, hospital), resource use in PICU and hospital resource use following
   PICU discharge: linear, Poisson or negative binomial regression models (as appropriate) and survival models
- A&E attendances: Poisson or negative binomial regression model (as appropriate)

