## 8.1.3.5 Sample size calculations

PICANet data from 2014/15 indicates that the 30-day mortality rate for transported PICU admissions is approximately 7% and that PICRTs reach critically ill children within 3 hours of referral acceptance in 85% of cases. Accounting for the potential for clustering of data by PICRTs, we calculate that a minimum of 9685 transports would allow us to detect a 3% difference in 30-day mortality between the two groups (transports taking ≥3 hours to reach patient bedside and transports taking <3 hours to reach patient bedside) with 80% power and alpha 5%. We will analyse PICANet data from transported PICU admissions over a 3-year period (nearly 15,000 transports) to ensure adequate sample size for our analysis.

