## 8.2.2 QUESTIONNAIRE STUDY

Clinical/research staff at each participating PICU will give a paper questionnaire to parents who consent to completing a questionnaire relating to the experience of PIC transport. Based on our ongoing research experience of collecting long term follow up information from children transported by the CATS team (BASIC, NIHR portfolio ID 15920) we will also offer parents the option to complete this questionnaire electronically using a secure online system (only centre and study numbers will be used; no identifiable data will need to be entered into the questionnaire). Wherever possible and relevant, both parents will be offered the opportunity to complete the

transport questionnaire individually if they were present for some of their child's transport to intensive care, recognising that parents may have different perspectives and capturing both viewpoints would enrich the description of family experiences.

We recognise that some patients will be from families who do not speak/write English and that these families may generally have a poorer experience of health care. Therefore, we will discuss with different PICRTs, and arrange for the information leaflet, consent form and transport questionnaire to be translated into the 5 most commonly spoken languages (other than English).

We will develop the questionnaire from similar existing questionnaires and from relevant literature, and use the experience of the study team, the steering group and parent representatives to further inform its format and content before it is finalised.

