#### 8.2.6 DATA ANALYSIS

Interview data will be entered into Framework, a matrix based approach, which facilitates rigorous and transparent data management. The method involves five distinct, but highly interconnected stages: familiarisation; identifying a thematic framework; indexing; charting; mapping and interpretation. The approach enables data to be examined within cases across a range of different themes, thereby facilitating comparisons to be made both between different models of retrieval and within PICRTs. Use of Framework is also well suited to research involving group- and individuallevel analysis. The data will be managed using NVivo, a qualitative data analysis programme. Questionnaire data will be analysed using descriptive statistics to describe and compare the different PICRT models and to examine associations between key variables (frequencies, medians and inter-quartile ranges, Spearman's correlations, Mann-Whitney, Chi-squared and Kruskall-Wallis analysis of variance, as appropriate).

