#### 8.3.4 ANALYSIS

Using these methods we will produce a patient-level dataset of costs and outcomes in the short-, medium- and long-run for every patient. Analyses of the mortality data will be as described above. QALYs will be analysed using a similar approach using linear models. Cost data are likely to be skewed and so to analyse these data (at 30 days, one year and lifetime) we will use a generalised linear model with gamma family and log link,[29] but will consider using other functional forms, such as Normal, Gaussian, inverse Gaussian and negative binomial distributions, selecting the model that gives the best fit of the data in terms of residual plots and the Akaike Information Criterion. We will also follow current guidance on conduct of economic evaluations using observational data to assess the main assumptions for addressing selection bias in the statistical models implemented.[30] The regression analyses will estimate lives saved, differences in costs, and QALYs gained between different PICRT models. Cost-effectiveness will be measured using incremental net monetary benefits (NMBs) calculated at different values of the willingness to pay to avoid one death or gain one QALY.

There will be considerable uncertainty in our estimates, especially in the long-run analysis. We will investigate this extensively using deterministic and probabilistic sensitivity analysis. Parametric and non-parametric bootstrap methods will be employed to evaluate uncertainty around differences in the lives saved, QALYs gained, costs and NMB, and we will construct cost-effectiveness acceptability curves.

The main outcome of the health economic analyses will be estimates of the costs and benefits of different PICRT models in the short-, medium- and long-run using a variety of cost and outcome measures, including point estimates and uncertainty intervals. We will follow current guidance for methods of technology appraisal to present and report the results of the economic analysis.[31] We will also estimate the budget impact if each PICRT model were to be rolled out nationally based on projections of need for PICRT services.

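### The cost model and bootstrap do not carry over the PICRT clustering that the protocol recognises elsewhere, and the questionnaire tests do not fit two forms from one family

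*Protocol*

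**What the plan says.** **Economic comparison.** Section 8.3.4 builds one record per patient and estimates lives saved, cost differences and QALYs gained between PICRT models. Mortality is analysed as in workstream A, and QALYs by a similar approach with linear models. Costs get their own specification: a generalised linear model with gamma family and log link. The alternatives listed are all distribution families, chosen by residual plots and AIC. For uncertainty the section says "Parametric and non-parametric bootstrap methods will be employed to evaluate uncertainty around differences in the lives saved, QALYs gained, costs and NMB", followed by acceptability curves. It does not say what unit is resampled.

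**Clustering elsewhere.** Section 7 says "The study will involve the participation of all 10 PICRTs and 24 PICUs in England and Wales". Section 8.1.3.4 (step 2) plans multilevel models where appropriate, "to include the random effects of PICU/PICRT/general hospital". Section 8.1.3.5 sizes the mortality comparison with clustering in mind: "Accounting for the potential for clustering of data by PICRTs, we calculate that a minimum of 9685 transports".

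**Questionnaires.** Under section 8.2.2, "both parents will be offered the opportunity to complete the" transport form individually, a change brought in by Amendment 1. Section 8.2.6 analyses the forms with descriptive statistics, Spearman correlations and "Mann-Whitney, Chi-squared and Kruskall-Wallis" procedures, as appropriate, including comparison of PICRT models. No family term or choice of one form per child is named.

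**The concern.** How a PICRT is organised is largely a property of the service, so a contrast between models draws its information mainly from the number of services, which is 10, and only secondarily from the number of children. If the cost regression and the bootstrap treat children as independent, variation between services that has nothing to do with the model is counted as evidence about the model. Costs enter every net monetary benefit, so the acceptability curves are exposed even where mortality and QALYs are modelled with a PICRT level. These results also feed the budget-impact estimate for national roll-out (section 8.3.4) and are combined with the service modelling (section 8.4.1).

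For the questionnaires, two parents describing the same transport will tend to agree. When the compared factor is shared by both, such as the PICRT model, counting their forms as two independent responses makes p-values too small.

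**Working it through.** **1. What the stated sample size implies about clustering.** Inputs from section 8.1.3.5: 30-day mortality about 7%, 85% of children reached within 3 hours, a 3-point difference, 80% power, alpha 5%, minimum 9685 transports. No ICC, design effect, sidedness or direction of effect is given, so 9685 cannot be reproduced from the stated inputs; it can only be solved backwards.

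Take 7% as the overall rate, the late group worse, and a two-sided test. Then 0.15·p1 + 0.85·p2 = 0.07 with p1 − p2 = 0.03 gives p1 = 9.55% and p2 = 6.55%. With k = 0.85/0.15 = 5.667:

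- n(late) = [1.96·√((1 + 1/k)·0.07·0.93) + 0.842·√(0.0955·0.9045 + 0.0655·0.9345/k)]² / 0.03²
- = (0.542 + 0.262)² / 0.0009 ≈ 720, so N = 720/0.15 = 4,800 without clustering.
- Implied design effect: 9685/4,800 = 2.02. With 968.5 transports per PICRT, ICC = (2.02 − 1)/967.5 ≈ 0.00105.

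Other readings of the inputs (10% vs 7%, 7% vs 4%, either direction) give an unclustered N of 3,267 to 5,540, or 3,527 to 5,794 with continuity correction. At the extremes:

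- 9685/3,267 = 2.96, ICC = 1.96/967.5 ≈ 0.0020
- 9685/5,794 = 1.67, ICC = 0.67/967.5 ≈ 0.0007

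So the plan's own number is consistent with a mortality ICC of roughly 0.0007 to 0.002.

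**2. Effect on a comparison of services.** Section 8.1.3.5 says "We will analyse PICANet data from transported PICU admissions over a 3-year period (nearly 15,000 transports"), about 1,500 per service if spread evenly over 10. Assume the exposure is fixed within service and the analysis ignores the service level. Design effect DE = 1 + 1,499·ICC; the standard error is too small by √DE; true coverage = 2Φ(1.96/√DE) − 1; a reported probability of cost-effectiveness of 0.95 corresponds to Φ(1.645/√DE).

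| Assumed ICC | DE | √DE | Coverage of nominal 95% | Reported 0.95 becomes |
|---|---|---|---|---|
| 0.0007 | 2.05 | 1.43 | 83% | 0.87 |
| 0.001 | 2.50 | 1.58 | 79% | 0.85 |
| 0.002 | 4.00 | 2.00 | 67% | 0.80 |

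A simulation of 5 against 5 services with 1,500 children each agrees: at ICC 0.002 the analysis that ignores services rejects a true null about 33% of the time, while a t-test on service means holds about 5%.

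**3. Questionnaires.** Let f be the share of responding families returning two forms and ρ the within-family correlation; neither is in the protocol. DE = 1 + ρ·2f/(1 + f), and the true level of a nominal 5% test is 2[1 − Φ(1.96/√DE)].

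- f = 20%, ρ = 0.3: DE = 1 + 0.3·0.4/1.2 = 1.10, true level about 6%; 800 forms carry the information of 727.
- f = 100%, ρ = 0.7: DE = 1 + 0.7·2/2 = 1.70, true level about 13%; 800 forms carry the information of 471.

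This is the worst case, where both forms of a family fall in the same comparison group.

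**The case against.** The protocol does not ignore clustering. It allows for PICRT clustering in the sample size, plans random effects in workstream A, and routes economic mortality and QALYs to that approach. A reader might infer that section 8.3.4 resamples patients as if independent and that all its intervals and curves are too confident. The text does not support that: the bootstrap unit is unstated, and only the cost model lacks the link to the multilevel approach. Section 8.1.3.4 also promises a statistical analysis plan, not shown here, which could settle the variance method. That reduces the force of the point but does not remove it: the promise is made under workstream A, and section 8.3.4 states its own cost model and its own alternatives, none hierarchical.

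The size is also open to challenge. The ICC is back-solved for mortality, and costs may behave differently. Section 8.3.1 bases the costing on team composition, interventions and critical incidents, which can vary between transports of one service; if a model is not fixed within service, the design effect is smaller. A larger cost ICC can be posited and gives far worse coverage, but no figure in the protocol supports one.

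For questionnaires, the plan is mainly descriptive, with tests to be used as appropriate and no stated hypothesis or alpha. That is fair. Still, every method named assumes independent responses, and the two-parent option was added deliberately.

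A reader might extend the point to PICU stay and organ support, recorded "during PICU stay, for each PICU admission", because no child-level term is named. The list of random effects is introduced with latitude, and the effect is minor: if 5% to 20% of children have two admissions with correlation 0.3 to 0.5 (assumed), the design effect is 1.03 to 1.17. The primary outcome uses the first admission only and is unaffected.

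**Conclusion.** The point holds in two parts. First, the cost model and the bootstrap in section 8.3.4 do not carry over the PICRT clustering recognised in sections 8.1.3.4 and 8.1.3.5, although the contrast is between models of only 10 services. If followed without a service level, standard errors would be about 1.4 to 2.0 times too small and nominal 95% intervals would cover about 67% to 83%. This assumes an ICC of 0.0007 to 0.002 taken from mortality as a guide, even service sizes, and a model fixed within service. Second, the methods in section 8.2.6 do not fit forms paired by family; a nominal 5% test would run at about 6% to 13% at worst, on assumed shares and correlations. Both parts concern secondary objectives. The plan should be corrected on both, but the primary mortality analysis is not in question.

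**What to change.** 1. **Section 8.3.4.** Specify a cost model with a PICRT random effect, or resample whole services and then patients within them, stratified by PICRT model. Apply this to every comparison of PICRT models, including net monetary benefit and the acceptability curves, with few-cluster inference (for example t-based intervals with service-level degrees of freedom). Stratification is needed because unstratified resampling of 10 services can lose a model: one with two services is absent from 0.8^10 ≈ 11% of replicates, and one with a single service from 0.9^10 ≈ 35%. State how many services form each model, and say so where a model has too few to support an interval.
2. **Section 8.2.6.** Use one form per child for testing, chosen by a rule set in advance, or use regression models with family-clustered standard errors. All forms can still be described.
3. **Optional.** Add a child-level term for outcomes recorded per admission.

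The cost is analysis wording and code; no further data are needed. The downside is wider intervals for the PICRT-model comparisons, possibly too wide to rank the models.

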## 8.4 Workstream D: Mathematical modelling

This work stream will address objective 2.2 of the DEPICT study:

Objective 2.2: To use mathematical modelling and location allocation optimisation methods to explore whether alternative models of service delivery for PICU/PICRT services can improve clinical outcomes without increasing overall cost.

This work will build directly on the quantitative analysis (work stream A) and the health economic evaluation (work stream C), but will also incorporate insights gained from the qualitative work (work stream B).

#### 8.4.1 APPROACH

The quantitative analysis (work stream A) will reveal which factors are the most important drivers of outcome for the child after emergency transport to PICU: for instance, this might be as specific as the distance the PICRT has to travel or the interventions provided by the PICRT once at the bedside. Or, the factors could be broader such as overall time to bedside or overall time from referral to PICU arrival. We will use mathematical modelling and optimisation methods to explore the potential impact on outcome of different possible models of service that could impact the identified drivers of better outcomes. For instance, possible alternative models could include:

- more transport services (to reduce distance) (either with same number of teams or more teams)
- the same number of transport services with more teams (to reduce time to bedside by having more teams available to go out)
- seasonal allocations of teams (to plan for the winter surge)
- changes to team composition, perhaps varying by region/season.

In such modelling, we will also use location-allocation optimization to investigate, for a given number of transport services and teams and a set of possible locations, where PICRTs should be based to minimise travel time to the local hospitals they serve and to the receiving PICUs. The constraints on the numbers of services, numbers of teams and possible locations will be defined through conversations with the PICRT services and commissioners.

Potential service models will also take into account the views of parents and staff, in particular where there are options that are clearly preferred and would not negatively affect the child's eventual outcome. Any proposed service models will be further re-examined in light of the feedback from stakeholders (parents and families, PICUs, PICRTs and local hospital clinicians) from the workshops (work stream E). We will also combine the results of this modelling strand with the cost-effectiveness analysis to explore how different potential models might affect the cost-effectiveness of the service.

#### 8.4.2 ESTABLISHING THE CORE DATASET AND DISTANCE/TIME LOOKUP TABLES

We will compile a dataset suitable for use in location/allocation analysis. This will involve collating data on the location of all hospitals in England and Wales that could act as a point of demand for transfer to a PICU and the location of PICUs themselves. We will explore gaining access to the SHAPE tool curated by Public Health England that contains these data (https://shape.phe.org.uk), including some detail on journey times between sites. Additionally, through discussion with commissioners and PICRT services, we will identify the set of potential locations for retrieval service teams, which will be a subset of the set of PICUs. We will also explore the approach used by Harper et al. for the Welsh ambulance service.[32] We will use their free tool, PatMap (https://github.com/JasYoung314/PatMap), to do this, which is based on Google Maps. This will result in a set of extensive look up tables containing the journey distances and expected journey times between potential locations of retrieval services, points of demand at local hospitals and PICUs.

## 8.4.3 SETTING UP A LOCATION MATHEMATICAL MODEL

Using the location/time dataset prepared earlier we will first develop a "coverage" discrete location model drawing on standard approaches from the operational research (OR) literature.[33] Essentially this coverage model will be used to identify the smallest set of PICRT locations and the attendant allocation of hospitals to PICRT "catchment areas" that ensures that each hospital is served by a PICRT positioned such that the distance travelled by retrieval teams or the time taken to retrieve sick children is below some threshold value. The use of travel distance or travel time and the choice of an acceptable threshold value will be informed by the statistical analysis in work stream A, the interviews in work stream B, and further discussion with key stakeholders. In this standard approach, we are looking for the fewest number of PICRT services that allow for full coverage of the country within defined time and distance constraints and then where they should be located.

